### 13.1.5 POOLABILITY ANALYSES

As poolability analyses, photopic monocular BCDVA and DCNVA in first operative eyes from the AAS observed data at Month 6 (Visit 4) will be summarized by treatment group and site using continuous summary statistics. Additionally, linear models will be fit with explanatory variables for site, treatment group, and site by treatment group interaction, including sites with 6 or more subjects. Sites with fewer than 6 subjects will not be arbitrarily pooled into a single larger site to be included in this model. If the site by treatment interaction is significant at a two-sided alpha = 0.15, then inferential statistics will be presented by site.

SAS® code similar to the code below will be used for the by site poolability analyses.

```
ods output tests3 = atest(where = (find(Effect, "SITEID") > 0)) lsmeans =
lsmeans diff = lsmean_diffs(where = (SITEID = _SITEID));
proc mixed data = indata;
  class trt SITEID;
  model AVAL = trt SITEID trt * SITEID / solution;
  lsmeans trt * SITEID / cl pdiff alpha = alpha;
run;

data lsmeans;
  set lsmeans;
  lsmean = estimate;
  se = StdErr;
run;

data lsmean_diffs;
  set lsmean_diffs;
  mean_diff = estimate;
  mean_diff_se = StdErr;
  mean_diff_ci_lcl = Lower;
  mean_diff_ci_ucl = Upper;
  test_stat = (estimate - theta0) / StdErr;
  pval = 2 * (1 - cdf("T", abs(test_stat), DF));
run;
```

where

- alpha = the type I error probability; 0.10 for BCDVA and alpha = 0.05 for DCNVA
- theta0 = value for difference in treatment group means under the null hypothesis; 0.10 for BCDVA and 0 for DCNVA

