### **8.4 Data Analysis Conventions**

All data analysis will be performed by [REDACTED]. Statistical programming and analyses will be performed using SAS® version 9.4 or higher. Output will be provided in rich text format (RTF) for tables and portable document format (PDF) for tables, listings, and figures using landscape orientation.

Summaries for continuous and ordinal variables will include the number of observations (n), arithmetic mean, SD, median, minimum, and maximum. Minima and maxima will be reported with the same precision as the raw values; means and medians will be presented to one additional decimal place than reported in the raw values. Standard deviations will be presented to two additional decimal places than reported in the raw values. Summaries for discrete variables will include counts and percentages. All percentages will be rounded to one decimal place (i.e., XX.X%). Differences between test and control treatment groups will be calculated as test minus control and change from baseline will be calculated as follow-up visit minus baseline.

All statistical tests will be one-sided with a significance level of 0.05 ( $\alpha = 0.05$ ), except for the two superiority tests of DCIVA and DCNVA which will be two-sided with a significance level of 0.05. Correspondingly, confidence intervals (CI) for differences between treatment groups will be two-sided at 90% or 95% confidence. All p-values will be rounded to 4 decimal places; p-values less than 0.0001 will be presented as “<0.0001”; p-values greater than 0.9999 will be presented as “>0.9999.”

Unless otherwise specified, summaries will be presented by treatment group and, where appropriate, visit. Listings will be presented by subject number, treatment group, visit/time point, and parameter as applicable.

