  class trt;
  var base aval_v3 aval_v4 aval_v5;
  MONOTONE REG(aval_v4 = aval_v3);
  MONOTONE REG(aval_v5 = aval_v4 aval_v3);
  MNAR MODEL(aval_v4 aval_v5 / MODELOBS=(trt= "2"));
run;

```

Thirty complete datasets will be generated from the above code.

A two-sample t-test will be performed for each imputed dataset and the results of the t-tests will be pooled using PROC MIANALYZE. SAS® code similar to the code below will be used to perform the primary analysis for each imputed dataset and then combine inferences across the imputed datasets:

```

proc sort data = mi;
  by _imputation_;
run;

ods output statistics = stat1(where = (Method ne
"Satterthwaite"));
proc ttest data = mi alpha = α
  by _imputation_;
  class trt;
  var aval_v4;
run;

proc sort data = stat1;
  by class _imputation_;
run;

ods output ParameterEstimates = pes;
proc mianalyze data = stat1 alpha = &alpha theta0 = &theta0;
  modeleffects Mean;
  stderr STDERR;
  by class;
run;

```

where

- $\&\alpha$ lpha = the significance level; 0.10 for BCDVA and 0.05 for DCNVA

- $\theta_0$  = the assumed difference in population means under the null hypothesis, 0.10 for BCDVA and 0 for DCNVA

After pooling the statistical analyses across the imputation datasets, the output dataset resulting from PROC MIANALYZE will contain means and standard errors for each treatment group and for the difference in treatment groups (test minus control), a CI for the treatment group difference (90% CI for BCDVA and 95% CI for DCNVA), and a two-sided p-value testing for whether the difference in treatment group means equals 0. These statistics from PROC MIANALYZE will comprise the primary effectiveness analyses for the primary effectiveness endpoints. If the upper confidence limit of the 90% confidence interval for the difference in treatment group means for BCDVA at Month 6 (Visit 4) is less than 0.1, then  $H_{0e}$  will be rejected in favor of  $H_{1e}$ , and the FINEVISION HP IOL will be considered to be statistically non-inferior to the AcrySof® SN60AT [REDACTED] IOL in BCDVA. If the two-sided p-value < 0.05 in favor of FINEVISION HP IOL for DCNVA at Month 6 (Visit 4), then the FINEVISION HP IOL will be considered to be statistically superior to the AcrySof® SN60AT [REDACTED] IOL in DCNVA.

The study will be considered a success only if both primary effectiveness endpoints are met.

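### The BCDVA p-values in the SAP are two-sided tests against the 0.10 margin, and Section 13.1 describes the pooled one as a test of zero difference

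*SAP*

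**What the plan says.** The BCDVA hypothesis is directional. SAP Section 3.5.1.1 sets the alternative as a test-minus-control difference below 0.10 logMAR, and Section 5.1.1 computes power for a one-sided t-test at 0.05. Section 8.4 gives the general rule: "All statistical tests will be one-sided with a significance level of 0.05". It exempts only the DCIVA and DCNVA superiority tests.

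In Section 13.1 the pooling step takes a null value, `theta0`, defined as "the assumed difference in population means under the null hypothesis, 0.10 for BCDVA and 0 for DCNVA". The paragraph that follows lists the output for both endpoints. It gives the interval level separately for each (90% for BCDVA, 95% for DCNVA), but describes one p-value for both: "a two-sided p-value testing for whether the difference in treatment group means equals 0". It counts these statistics as the primary effectiveness analyses. Non-inferiority in BCDVA is then declared if the upper 90% limit is below 0.1.

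Section 13.1.5 covers consistency across sites: "If the site by treatment interaction is significant at a two-sided alpha = 0.15, then inferential statistics will be presented by site". Its code computes "test_stat = (estimate - theta0) / StdErr", with "theta0 = value for difference in treatment group means under the null hypothesis; 0.10 for BCDVA and 0 for DCNVA", and then "pval = 2 * (1 - cdf('T', abs(test_stat), DF" with the brackets closed. The same data step outputs the site difference and its confidence limits, at "alpha = the type I error probability; 0.10 for BCDVA and alpha = 0.05 for DCNVA".

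**The concern.** There are two faults with one source.

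First, the description in 13.1 is right for DCNVA, where the null is 0, and wrong for BCDVA, where it is 0.10. Someone relying on that sentence would take a very small BCDVA p-value as evidence that the lenses differ in distance acuity. In fact it measures how far the estimate lies from the margin.

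Second, taking the absolute value and doubling the tail turns a directional question (is the difference below 0.10?) into a non-directional one (is it different from 0.10?). A small value can then come from a result well inside the margin or from one well beyond it. By-site inference is shown only when treatment effects appear to differ between sites, which is when direction matters most.

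The Section 13.1 method is reused for BCDVA in the sensitivity analyses (13.1.1 to 13.1.3), the pupil-size subgroups (13.1.4) and the Month 12 repeat (14.1), so the wrong description would carry over to those results.

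**Working it through.** **Inputs from the documents.** 300 test and 150 control eyes, SD 0.10, margin 0.10, true difference 0, one-sided 0.05 (SAP 5.1.1); 501 subjects, up to 24 sites, 2:1 allocation (SAP 4.1, 5); `theta0` = 0.10 for BCDVA (SAP 13.1, 13.1.5).

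**Assumptions.** The documents give no per-site counts by arm and no model degrees of freedom. The SE of 0.05 with 430 df is illustrative. As a range I also use sites of 14/7 (501/24 is about 21), 20/10, and 4/2 (the six-subject minimum for the site model). For these, df is 453 = 501 - 48 site-by-arm cells, with within-site df as a check. The pooled example ignores imputation variance.

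**The plan's own figure.** SE = 0.10 × √(1/300 + 1/150) = 0.0100. The margin is 10 standard errors from the assumed truth, so power is effectively 100%, in line with the stated figure of more than 99%.

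**Pooled p-value, 13.1.** With d the observed difference, t = (d - null)/0.0100 on 448 df, two-sided:

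| d | p as coded (null 0.10) | p as described (null 0) |
|---|---|---|
| 0.00 | t = -10, <0.0001 | t = 0, 1.00 |
| 0.02 | t = -8, <0.0001 | t = 2, 0.046 |
| 0.10 | t = 0, 1.00 | t = 10, <0.0001 |
| 0.20 | t = 10, <0.0001 | t = 20, <0.0001 |

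Code and description answer different questions. As coded, d = 0.00 and d = 0.20 give the same value.

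**By-site p-value, 13.1.5.** t = (d - 0.10)/SE; coded p = 2 × [1 - F(|t|)]; the directional p that matches the alternative is F(t), where F is the t distribution function.

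With SE 0.05 and 430 df:
- d = -0.05: t = -0.15/0.05 = -3; coded p 0.003; directional p 0.001.
- d = +0.25: t = 0.15/0.05 = +3; coded p 0.003; directional p 0.999.

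Range over site sizes (SD 0.10, 453 df):

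| Site (SE) | d | Coded p | Directional p | 90% CI |
|---|---|---|---|---|
| 14/7 (0.0463) | 0.00 | 0.031 | 0.016 | -0.076 to 0.076 |
| 14/7 | 0.20 | 0.031 | 0.984 | 0.124 to 0.276 |
| 14/7 | -0.05 | 0.0013 | 0.0006 | -0.126 to 0.026 |
| 14/7 | 0.25 | 0.0013 | 0.9994 | 0.174 to 0.326 |
| 20/10 (0.0387) | 0.00 | 0.010 | 0.005 | -0.064 to 0.064 |
| 20/10 | 0.20 | 0.010 | 0.995 | 0.136 to 0.264 |
| 4/2 (0.0866) | 0.00 | 0.249 | 0.124 | -0.143 to 0.143 |
| 4/2 | 0.20 | 0.249 | 0.876 | 0.057 to 0.343 |

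With 19 df, the coded p at the 14/7 site is 0.044 for d = 0.00 and 0.20, and 0.0043 for d = -0.05 and 0.25. The symmetry holds at every size, but at the smallest sites the shared p-value is not small. It is exact only for equal SEs and estimates symmetric about 0.10.

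**The case against.** The strongest reply is that nothing is decided on these p-values. That stands. BCDVA success is read from the upper 90% limit, so a reader who infers inflated type I error, lost power or a wrong study conclusion goes further than the documents allow.

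A reader might also infer that the by-site output cannot tell a failing site from a passing one. The documents do not support that. The same code outputs the estimate and the 90% interval. In the SE 0.05 example the intervals are about -0.13 to 0.03 and 0.17 to 0.33, which could not be confused. By-site inference appears only if the interaction passes the 0.15 screen, and Protocol 9.4.7 then asks for its cause to be evaluated; it sets no non-inferiority test by site.

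A third tempting reading is that the coded p-value contradicts the interval. At a 14/7 site with t = -1.8, the upper limit is 0.093 (non-inferior) while the coded p is 0.073. Against the alpha of 0.10 that 13.1 and 13.1.5 set for BCDVA, there is no conflict: below the margin, a two-sided p under 0.10 is the same decision as a one-sided p under 0.05. Only a reader using the 0.05 of Section 8.4 would see one. The wrong-direction case remains at either level.

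Finally, the code is offered as a pattern, the correct BCDVA null is stated shortly before the faulty sentence, and the table shells are not visible, so how the tables would label the value is unknown. These points limit the harm. They do not make the sentence or the formula right for BCDVA.

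**Conclusion.** The point holds as an error in reported p-values and their description, for BCDVA only. Section 13.1 describes as a test of zero a value computed against 0.10. At an observed difference of 0 with 300/150 eyes and SD 0.10, that means below 0.0001 where a test of zero gives 1.00. Section 13.1.5 reports a non-directional p-value for a directional hypothesis, contrary to Sections 3.5.1.1 and 8.4, so sites on opposite sides of the margin can share a p-value.

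The pooled example depends on the plan's SD and on full data. The by-site sizes depend on assumed SEs and df, but the loss of direction follows from the formula alone. The study decision, its error rate and its power are unchanged. This is a low-priority correction, worth making because the SAP contradicts itself on a co-primary endpoint.

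**What to change.** For BCDVA only, choose one of two routes.

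1. Report the lower-tail p-value against 0.10: `cdf('T', test_stat, DF)` by site, and its equivalent from the pooled result (half the two-sided value if t is negative, one minus half if t is positive). Judge it at one-sided 0.05.
2. Omit BCDVA p-values and rely on the 90% interval. This is simpler and loses nothing the decision rule uses.

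Under either route, reword the sentence in 13.1 so that the null difference is 0.10 for BCDVA (if a p-value is kept) and 0 for DCNVA. State in 13.1 and 13.1.5 that alpha 0.10 sets only the 90% interval level; otherwise a one-sided p-value could be compared with 0.10. Because the by-site p-value line also serves DCNVA, make it endpoint-specific. Keep the two-sided formula against 0 for DCNVA and DCIVA.

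The cost is a conditional code line by site, a short step after pooling, one reworded sentence and a note on alpha in two places. Data collection, sample size and the decision rule do not change.

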### 13.2 Secondary Analyses

The secondary effectiveness endpoint is:

- Photopic monocular logMAR intermediate (66 cm) visual acuity with distance correction (DCIVA) in first operative eyes at Month 6 (Visit 4)

The secondary effectiveness endpoint will be based on the AAS. The primary analysis for DCNVA will be repeated for photopic DCIVA (66 cm) in first operative eyes at Month 6 (Visit 4). If the two-sided p-value < 0.05 in favor of FINEVISION HP IOL for DCIVA, then the FINEVISION HP IOL will be considered to be statistically superior to the AcrySof® SN60AT [REDACTED] IOL in DCIVA.

Inference will be conducted for the secondary effectiveness analysis only if all primary effectiveness endpoints are met.

The sensitivity analyses for DCNVA will also be repeated for photopic DCIVA (66 cm) in first operative eyes at Month 6 (Visit 4).

Subgroup and poolability analyses of photopic monocular DCIVA (66 cm) in first operative eyes from the AAS at Month 6 (Visit 4) will be performed similarly as those for DCNVA.

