	DCNVA (40 cm)	Photopic	Monocular					X	X	X	X
			Binocular					X	X	X	X
	UCIVA (66 cm)	Photopic	Monocular					X	X	X	X
			Binocular						X	X	X

			Visit 0	Visit 00 A	Visit 00 B	Visit 1 A/B	Visit 2 A/B	Visit 3 A/B	Visit 4	Visit 5	USV 
Examination	Light Condition	Monocular / Binocular	Pre-Op / Screen D -90 to -1	Implant A  D 0	Implant B  (D 7 to D 30 after Visit 00 A)	Post-Op D 1-2	Post-Op D 7-14	Post-Op D 30-60	Post-Op D 150-180 (from 1 st eye)	Post-Op D 360-420 (from 1 st eye)	N/A
DCIVA (66 cm)	Photopic	Monocular							X	X	X
		Binocular							X	X	X
		Monocular							X	X	X
		Binocular							X	X	X
Contrast Sensitivity with Glare – 2.5 meters	Photopic	Monocular								X	X
Contrast Sensitivity without Glare – 2.5 meters										X	X
Contrast Sensitivity with Glare – 2.5 meters	Mesopic	Monocular								X	X
Contrast Sensitivity without Glare – 2.5 meters										X	X
Defocus Curve (Best Distance Corrected) – 4 meters 	Monocular								X	X	
	Binocular								X	X	

 A – First Operative Eye, B – Second Operative Eye

 USV – Unscheduled Visit; for unscheduled visits, mandatory assessments to be completed are defined in the table. Additional assessments may be performed as appropriate, based on the subject's condition.

 Patient Reported Outcome Questionnaires include the PRSIQ, QoV and QoV Supplemental Questions

			Visit 0	Visit 00 A	Visit 00 B	Visit 1 A/B	Visit 2 A/B	Visit 3 A/B	Visit 4	Visit 5	USV 
Examination	Light Condition	Monocular / Binocular	Pre-Op / Screen D -90 to -1	Implant A  D 0	Implant B  (D 7 to D 30 after Visit 00 A)	Post-Op D 1-2	Post-Op D 7-14	Post-Op D 30-60	Post-Op D 150-180 (from 1 st eye)	Post-Op D 360-420 (from 1 st eye)	N/A

 Pupil size measurements in mesopic and photopic lighting conditions must be taken right before contrast sensitivity testing (see instructions for Pupil Size Measurements in Manual of Procedures)

[REDACTED]

[REDACTED]

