### Primary Strategy

1. Withdrawal due to physician decision: missing data assumed to be MNAR. Control-based multiple imputations will be completed for superiority hypotheses and treatment-based multiple imputations will be completed for non-inferiority hypotheses. [hypothetical strategy]
2. Missing data without withdrawal or withdrawal due to reasons other than due to physician decision: missing data assumed to be MAR. Treatment-based multiple imputations will be completed. [hypothetical strategy]

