## **13. Effectiveness Analyses**

### **13.1 Primary Analyses**

The co-primary effectiveness endpoints are:

- Photopic monocular logMAR best corrected distance visual acuity (BCDVA) in first operative eyes at Month 6 (Visit 4)
- Photopic monocular logMAR near visual acuity with distance correction (DCNVA) in first operative eyes at Month 6 (Visit 4)

The primary analyses of the primary effectiveness endpoints will be based on the AAS with intercurrent events handled using the primary strategy presented in [Section 8.2](#).

If a subject has no observed data for an endpoint at any of the scheduled visits (e.g. subject exits study prior to Month 1 [Visit 3A] study visit and therefore has no DCNVA data), the endpoint will be imputed at the earliest scheduled visit as a normal random variable with mean equal to the respective treatment group mean and SD equal to the respective treatment group SD based on observed data for the respective treatment group at the earliest scheduled visit for that endpoint. If the imputed value is less than the minimum observed value within the respective treatment group or greater than the maximum observed

value within the respective treatment group, the imputed value will be set equal to the minimum or maximum value, respectively. This initial imputation procedure will be performed for BCDVA using SAS® code similar to the code below:

```

proc means data = indata noprint;
  var base;
  by trt;
  output out = A3_stats(drop = _TYPE_ _FREQ_) mean = mean std
= sd min = min max = max;
run;

data indata(drop = mean sd min max Z);
  call streaminit(938428);
  merge indata indata_stats;
  by trt;

  if cmiss(base, aval_v2, aval_v3, aval_v4, aval_v5) = 5 then
do;
  Z = round(rand('Normal', mean, sd), 0.02);
  if Z > max then Z = max;
  else if Z < min then Z = min;
  base = Z;
end;
run;

```

where

- trt = treatment group coded as 1 for the test IOL and 2 for the control IOL
- base = BCDVA at baseline
- aval\_vi = BCDVA at Visit i, i = 2, 3, 4, and 5.

Similar code as above will be used for DCNVA with "base" replace by "aval\_v3" in the means procedure block of code and the data step cmiss if-condition updated to "if cmiss(aval\_v3, aval\_v4, aval\_v5) = 3" and clause "base = Z" updated to "aval\_v3 = Z".

Non-monotone missing data for BCDVA will first be multiply imputed using treatment-based MCMC methodology similarly as in the SAS® code below:

```

/* Impute non-monotone missing data using treatment-based MCMC

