for the first operative eye*/
proc mi data = indata out = mcmc nimpute = 30 seed = 891567 round
= 0.02;
  by trt;
  mcmc impute = monotone;
  var base aval_v2 aval_v3 aval_v4 aval_v5;
run;

```

Similar code as above will be used for DCNVA with the variables in the var statement updated to "aval\_v3 aval\_v4 aval\_v5".

Monotone missing data will be imputed for BCDVA using treatment-based re

BCDVA using SAS® code similar to the code below:

```
/* Treatment-based monotone regression imputation */
proc mi data = mcmc out = mi n impute = 1 seed = 891568 round =
0.02;
  by trt _imputation_;
  var base aval_v2 aval_v3 aval_v4 aval_v5;
  MONOTONE REG(aval_v2 = base);
  MONOTONE REG(aval_v3 = aval_v2 base);
  MONOTONE REG(aval_v4 = aval_v3 aval_v2 base);
  MONOTONE REG(aval_v5 = aval_v4 aval_v3 aval_v2 base);

run;
```

After imputation of non-monotone missing data, the DCNVA data will be partitioned into a dataset containing missing data due to withdrawal due to physician decision and a data set containing the remaining DCNVA data, including missing data due to any other reason:

```
/* Split mcmc into cases where missing is due to withdrawal due
to physician decision or other */
data mcmc1;
  set mcmc (where = (DSDECOD ne "Physician Decision"));
run;

data mcmc2;
  set mcmc (where = (DSDECOD = "Physician Decision"));
run;
```

where

- DSDECOD = reason for discontinuation.

The monotone missing data not due to withdrawal due to physician decision will be imputed using treatment-based regression methodology using SAS® code similar to the code below:

```
/* Impute missing data not due to Physician Decision using
treatment-based regression methodology */
proc sort data = mcmc1;
  by PARAMCD &trt. _imputation_;
run;

proc mi data = mcmc1 out = mil n impute = 1 seed = 891568 round =
0.02;
  by PARAMCD &trt. _Imputation_;
  var aval_v3 aval_v4 aval_v5;
  monotone reg(aval_v4 = aval_v3);
  monotone reg(aval_v5 = aval_v4 aval_v3);

run;
```

The resulting imputed data will then be combined with the missing data due to withdrawal due to physician decision. If there is any missing data due to withdrawal due to physician decision, it will be imputed using control-based regression methodology using SAS® code similar to the code below:

```

data mcmc2;
  set mil mcmc2;
run;

proc sort data = mcmc2;
  by _imputation_;
run;

/* Control-based monotone regression imputation */
proc mi data = mcmc out = mi nimpute = 1 seed = 891568 round =
0.02;
  by _imputation_;

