## 25. Appendix

### 25.1 Schedule of Visits and Assessments

			Visit 0	Visit 00 A	Visit 00 B	Visit 1 A/B	Visit 2 A/B	Visit 3 A/B	Visit 4	Visit 5	USV 
Examination	Light Condition	Mono-cular / Binocular	Pre-Op / Screen D -90 to -1	Implant A  D 0	Implant B  (D 7 to D 30 after Visit 00 A)	Post-Op D 1-2	Post-Op D 7-14	Post-Op D 30-60	Post-Op D 150-180 (from 1 st eye)	Post-Op D 360-420 (from 1 st eye)	N/A
Informed Consent and HIPAA			X								
Demographics			X								
Inclusion & Exclusion Criteria Evaluation			X								
Inclusion & Exclusion Criteria Review				X							
Ocular and non-ocular Medical History			X	X	X	X	X	X	X	X	X
Urine Pregnancy Test (if applicable)			X								
Projected Visual Acuity			X								
Target Refraction			X								
IOL Power Calculation			X								
Axial Length and Anterior Chamber Depth			X								
Keratometry Measurement			X					X	X	X	X
Corneal Topography			X								
Manifest Refraction (ETDRS) – 4 meters			X				X	X	X	X	X
Randomization			X								
Operative Procedures				X	X						
Patient Reported Outcome Questionnaires 			X						X	X	X
Pupil Size 	Photopic	Monocular	X						X	X	
	Mesopic		X						X	X	
Intraocular Pressure			X			X	X	X	X	X	X
Slit Lamp Examination			X			X	X	X	X	X	X
IOL Tilt and Decentration Grading						X	X	X	X	X	X
[REDACTED]				█	█	█	█	█	█	█	█

			Visit 0	Visit 00 A	Visit 00 B	Visit 1 A/B	Visit 2 A/B	Visit 3 A/B	Visit 4	Visit 5	USV 
Examination	Light Condition	Mono-cular / Binocular	Pre-Op / Screen D -90 to -1	Implant A  D 0	Implant B  (D 7 to D 30 after Visit 00 A)	Post-Op D 1-2	Post-Op D 7-14	Post-Op D 30-60	Post-Op D 150-180 (from 1 st eye)	Post-Op D 360-420 (from 1 st eye)	N/A
Dilated Fundus Examination			X						X	X	X
Posterior Capsule Assessment (PCO grade assessment)						X	X	X	X	X	X
IOL Observations						X	X	X	X	X	X
Adverse Events			X	X	X	X	X	X	X	X	X
Device Deficiencies				X	X	X	X	X	X	X	X
Concomitant Medications			X	X	X	X	X	X	X	X	X
Exit from Study											X
Visual Acuity	UCDVA (4 meters)	Photopic	Monocular	X			X	X	X	X	X
			Binocular					X	X	X	X
	BCDVA (4 meters)	Photopic	Monocular	X				X	X	X	X
			Binocular					X	X	X	X
	UCNVA (40 cm)	Photopic	Monocular						X	X	X
			Binocular						X	X	X
	BCNVA (40 cm)	Photopic	Monocular						X	X	X
			Binocular						X	X	X
	DCNVA (40 cm)	Photopic	Monocular						X	X	X
			Binocular						X	X	X
		Mesopic	Monocular						X	X	X

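### SAP 13.2 carries over to DCIVA an imputation that predicts Visit 4 from Visit 3, but the protocol schedule has no Visit 3 DCIVA; the schedules need reconciling and DCIVA may need its own model

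*SAP*

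**What the plan says.** SAP 13.2 defines the analysis of DCIVA at 66 cm by reference: "The primary analysis for DCNVA will be repeated for photopic DCIVA (66 cm) in first operative eyes at Month 6 (Visit 4". It gives no variable list or imputation model for DCIVA.

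The analysis it refers to is in SAP 13.1. For DCNVA the imputation variables are the values at Visits 3, 4 and 5, and Month 6 is predicted from Month 1 alone: "MONOTONE REG(aval_v4 = aval_v3". A subject with no data on an endpoint gets a starting value before PROC MI is called: "the endpoint will be imputed at the earliest scheduled visit as a normal random variable with mean equal to the respective treatment group mean". The SAP's own example shows that DCNVA is taken to begin at Month 1: "subject exits study prior to Month 1 [Visit 3A] study visit and therefore has no DCNVA data".

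SAP 8.2 covers the primary and secondary effectiveness analyses. For withdrawals by physician decision it states: "Control-based multiple imputations will be completed for superiority hypotheses".

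In the protocol schedule (1.3) the two acuities have different rows: "DCNVA (40 cm) Photopic Monocular X X X X" against "DCIVA (66 cm) Photopic Monocular X X X". In the SAP appendix (25.1) the DCNVA row has lost a mark, "DCNVA (40 cm) Photopic Monocular X X X", and the DCIVA row has its marks in the same positions.

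**The concern.** If DCIVA is first measured at Visit 4, the borrowed regression has no predictor, and Visit 4 becomes both the endpoint visit and the earliest scheduled visit. Carrying the stated rules over would then have two effects.

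- Any subject with neither a Visit 4 nor a Visit 5 value receives one random draw from his or her own arm at the endpoint visit, whatever the reason for leaving. Visit 4 is then no longer missing, so the control-based step has nothing to act on there. A physician-decision withdrawal in the test arm receives a test-arm value, which favours superiority.
- The draw is made once, before the 30 imputed datasets are created. It is the same in all of them, so its uncertainty never enters the pooled standard error.

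DCIVA is the only secondary effectiveness hypothesis and belongs to the Type I error hierarchy of SAP 8.5. Its missing-data method should be settled before unmasking. SAP 13.2 also repeats the DCNVA sensitivity analyses for DCIVA, so the ITT and Best Case analyses inherit the gap.

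**Working it through.** **1. Which visits carry DCIVA?** The visit columns are 0, 00A, 00B, 1, 2, 3, 4, 5 and unscheduled: nine in all.

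- *Protocol 1.3.* The photopic monocular DCIVA row follows a repeated full header and has nine visit cells: six empty, then marks at Visit 4, Visit 5 and unscheduled. On the same page, contrast sensitivity falls at Visit 5 and unscheduled, and the defocus curves at Visits 4 and 5. Both agree with the analysis text, so the columns there appear aligned. DCNVA and UCIVA monocular each have four marks, which fit Visits 3, 4, 5 and unscheduled.
- *SAP 25.1.* The photopic monocular DCNVA and DCIVA rows each have only eight cells, with marks in cells 6 to 8. Counted from the left, both start at Visit 3. Counted from the right, both start at Visit 4, which contradicts SAP 13.1 for DCNVA.

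**2. The plan's own power figure (SAP 5.3.1).** Inputs: 300 and 150 eyes, difference -0.10, SD 0.14, two-sided alpha 0.05.

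SE = 0.14 × sqrt(1/300 + 1/150) = 0.0140, and noncentrality = 0.10/0.0140 = 7.14. Power exceeds 99.99%, in agreement with the stated figure of more than 99%.

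**3. Standard error if Visit 4 is filled by one own-arm draw.** Let f be the fraction of eyes with neither Visit 4 nor Visit 5 DCIVA, equal in both arms. With n eyes in an arm, the completed mean is (1-f) × observed mean + f × mean of the draws. Its variance is

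s²/n × [1/(1-f) + f],

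while the analysis reports s²/n. The ratio of true to reported SE is r = sqrt(1/(1-f) + f), and the actual two-sided error is 2 × [1 - Φ(1.96/r)].

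| f (assumed) | r | actual error at nominal 0.05 |
|---|---|---|
| 2% | 1.020 | 0.055 |
| 5% | 1.050 | 0.062 |
| 10.2% | 1.103 | 0.075 |

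The last row takes the plan's whole loss: 51/501 = 34/334 = 17/167 = 10.2%. A simulation with 300 of 334 and 150 of 167 eyes observed, and draws truncated to the observed range as SAP 13.1 specifies, gave 0.073.

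**4. Size of the bypassed control-based rule.** If a fraction f of the test arm were physician-decision withdrawals with no DCIVA, the intended expected difference would be -0.10 × (1-f). That is -0.098, -0.095 or -0.090 at f = 2%, 5% or 10.2%, against -0.100 under own-arm draws. Power under the attenuated difference stays above 99.9% in each case.

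**The case against.** The strongest reply is that the SAP appendix, counted from the left, fits the SAP's own code: BCDVA begins after surgery at Visit 2, DCNVA at Visit 3, and monocular DCIVA at Visit 3. The DCNVA model would then run for DCIVA as written. A reader might infer from the protocol table alone that the secondary analysis cannot be run at all. The documents do not support that. What they show is an apparent conflict between two schedules, both read from PDF.

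The appendix does not settle the matter the other way, however. Counted from the left, its UCDVA row would start at Visit 1, and its monocular distance-acuity rows would have no unscheduled-visit mark, although protocol 8.4 makes UCDVA and BCDVA mandatory at those visits. It also lacks the Visit 3 fundus mark that SAP 16.9 requires. SAP Section 1 gives the SAP's statistical methods precedence over the protocol's, but that cannot create a measurement the sites were not scheduled to take.

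A second reply is that the SAP code is only illustrative, that it already shortens the variable list between BCDVA and DCNVA, and that 8.2 states the control-based rule in general terms. This stands in part. A programmer could honour 8.2, and subjects who miss Visit 4 but attend Visit 5 would still be imputed by MCMC. But the order of steps in 13.1 puts the draw first, and nothing tells the programmer to depart from it for DCIVA.

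A third reply is that 10% overstates f. That is correct. It is total loss to Month 12, and the All-Implanted Analysis Set already excludes eyes with no postoperative visit.

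**Conclusion.** The point holds in a limited form. SAP 13.2 relies on a Visit 3 value that the protocol schedule does not provide and that the SAP appendix only appears to provide. On the protocol schedule, the stated rules carried over as they stand would replace multiple imputation at the endpoint visit with a single own-arm draw and leave the control-based rule of 8.2 unapplied there. The true standard error would be about 2%, 5% or 10% larger than reported at f = 2%, 5% or 10%.

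This rests on three assumptions: that the protocol columns are read correctly, that the earliest-visit rule is carried over unchanged, and that f lies in the range shown, with 10% as an upper bound. The documents give neither the timing of losses nor the share due to physician decision.

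A reader might also infer that the superiority claim for DCIVA is in doubt. At the planned effect it is not: power is above 99%, and even the upper-bound attenuation, to -0.090, leaves it above 99.9%. The fault lies in prespecification and in the accuracy of the reported interval. It should be corrected, but it is unlikely to change the conclusion.

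**What to change.** First, confirm whether photopic monocular DCIVA is measured at Visit 3, make protocol 1.3 and SAP 25.1 agree, and list the DCIVA visits in SAP 13.2.

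- **If DCIVA starts at Visit 4:** state in SAP 13.2 that the starting-value rule is not applied to the Visit 4 value. Impute Visit 4 DCIVA within each of the 30 imputations from first-eye acuities already taken at Visit 3, for example UCIVA at 66 cm, DCNVA and BCDVA. Do this by treatment group for the cases assumed missing at random, and with `MNAR MODEL` and `MODELOBS=(trt='2')` for physician-decision withdrawals. The choice of predictors is open; keeping the control-based rule and the imputation uncertainty is the essential part.
- **If DCIVA is measured at Visit 3:** correct the protocol schedule and keep the DCNVA model.

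The cost is one SAP paragraph with a changed variable list, or one corrected schedule row. Neither adds an assessment.
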